The adherence and persistence among those initiating SGLT2i and GLP-1 RA medications 6-months after the first medication fill will be described. Adherence to either class of medication will be measured as proportion of days covered [PDC] among those initiating treatment. The PDC will be the days' supply of medication divided by the number of days total in the follow-up. This will be described as a continuous measure (mean (SD), median (IQR), range) as well as categorically (e.g., $\geq 80\%$ and $< 80\%$ or other categorizations as appropriate). Persistence to the index medications will be defined as non-discontinuation of the treatment. A patient will be considered non-persistent if there is a > 90 day gap in therapy and persistent if there are no gaps in therapy or gaps in therapy of ≤ 90 days. Adherence and persistence may also be assessed at 12-months post-initiation based on results of 6-month measure.

Limitations

- Generalizability will be limited to the Humana MAPD population in the East region. However, the insights from this pilot may be used to inform and scale similar endeavors to other regions or populations.
- We cannot determine instances where a physician prescribed a treatment but the patient did not fill it (and why) or if a patient filled a prescription outside the data sources available to Humana (misclassification bias). Additionally, if patients do not stay enrolled in the health plan through the outcome observation period, then their outcomes may be misclassified as their data would not be available to capture. However, sensitivity analyses are planned to attempt to assess the impact of this bias.
- There may be barriers for providers to prescribe and/or patients to initiate and/or adhere to treatment, including factors related to increased member costs, not able to be ascertained from claims.
- Potential early adoption of an approved PQA measure linked with a risk arrangement in the region may impact outcomes. The study will randomize among patients and providers in different risk arrangements at the outset of the study and plan to conduct a subgroup analysis across arrangements.

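### Adherence is called proportion of days covered but is defined as days' supply over follow-up days, a possession ratio that can exceed 100% and lift patients over the example 80% cut

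*Combined protocol and SAP*

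**What the plan says.** All the relevant text is in the adherence and persistence paragraph of the Statistical Analysis Plan, Secondary Objectives.

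- The population and time frame: "The adherence and persistence among those initiating SGLT2i and GLP-1 RA medications 6-months after the first medication fill will be described".
- The measure is named: "Adherence to either class of medication will be measured as proportion of days covered [PDC] among those initiating treatment".
- The next sentence defines it as the days' "supply of medication divided by the number of days total in the follow-up".
- The reporting: "This will be described as a continuous measure (mean (SD), median (IQR), range) as well as categorically", with 80% offered as an example cut and other groupings allowed.

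The paragraph sets no maximum. It gives no rule for supply that runs past the end of follow-up, for early refills, or for patients who switch between the two classes or take both. The Study Design section and the Secondary Outcome Measures list name the outcome without giving another formula.

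**The concern.** The name and the definition describe different quantities. Proportion of days covered asks on what share of days the patient had drug on hand. The stated formula asks how much drug was dispensed relative to the length of follow-up. The two agree only when all dispensed supply is used inside the window, one day's supply at a time.

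If the sentence is programmed as it stands, three things follow. The mean and range can include values above 100%. A patient with a refill gap of more than a month can be counted as adherent at the 80% cut. And supply of two classes held on the same days is counted twice, because the measure pools either class. All three push adherence upward, and the result would carry a label that readers take to mean something else.

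**Working it through.** The documents give no adherence figure, so there is nothing to reproduce. The check applies both definitions to constructed fill histories.

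**Inputs.** From the plan: the formula, a 6-month follow-up from first fill, pooling of the two classes, and the example 80% cut. Assumed, because the plan does not give them: a window W of 180 to 184 days for 6 months, fill sizes of 30 or 90 days, and the fill dates.

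**Formulas.**
- As written: R = (sum of days' supply of fills in the window) / W.
- Days covered: C = (distinct days in the window with drug on hand) / W.

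Each covered day uses at least one dispensed day's supply, so C is never above R. C cannot exceed 1, while R has no upper limit.

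**One drug.**

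| Fill history | R (W = 184 to 180) | C over the same windows |
|---|---|---|
| 90-day fills on days 0, 80, 160 | 270/W = 1.47 to 1.50 | 1.00 |
| Eight 30-day fills, every 25 days | 240/W = 1.30 to 1.33 | 1.00 |
| Two 90-day fills, days 0 and 127 | 180/W = 0.98 to 1.00 | 147/184 = 0.799 to 143/180 = 0.794 |
| 30-day fills on days 0, 30, 60, 90, 160 | 150/W = 0.82 to 0.83 | 144/184 = 0.783 to 140/180 = 0.778 |
| Six 30-day fills, on time | 180/W = 0.98 to 1.00 | the same |

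The last row shows that the definitions agree when fills are on time and end inside the window.

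**Where the 80% cut is crossed.** Take two 90-day fills, the second on day r, with r later than W − 90. Then R = 180/W whatever r is, and C = (90 + W − r)/W. C falls below 0.80 when r exceeds 90 + 0.2W, which is 126 for W = 180 and 126.8 for W = 184. So a second fill on day 127 or later, a gap of at least 127 − 90 = 37 days, gives C below 0.80 in every window while R stays at 0.98 to 1.00. If the second fill falls on the last day, C = 91/W = 0.49 to 0.51 and R is unchanged.

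**Two classes (W = 180).**
- Three consecutive 30-day fills of both classes together: R = 180/180 = 1.00; C = 90/180 = 0.50.
- 90 days of one class on day 0, then 90 days of the other on day 30: R = 180/180 = 1.00; C = 120/180 = 0.67.

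**The case against.** The strongest reply is that the sentence is a one-line gloss on a well-known measure. It refers to days' supply without saying that supply is summed over all fills, and a programmer could follow the name and run a standard PDC algorithm. That is possible, and it limits how firmly one can say what will be computed. It does not rescue the text: nothing in the documents says the formula is shorthand, and summing supply across fills is its natural reading.

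The second reply is about weight, and it stands. The plan describes adherence among initiators and sets out no between-arm test of it. The 80% cut is only an example.

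A reader might go further and infer that a large share of initiators would be misclassified. The documents give no refill pattern, so they do not support this. Under an assumed model (exponential refill delays, no early refills, no permanent stop), the share wrongly placed at or above 80% runs from below 0.1% to 35–38%, depending on fill size and mean delay. Allowing a 10% or 20% chance of stopping after each fill lowers that top figure to about 23–25% or 15–16%. These figures reflect the assumptions and say nothing specific about this trial.

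A reader might also infer that the rest of the paragraph is faulty. The documents do not establish that either:
- The persistence rule ("A patient will be considered non-persistent if there is a > 90 day gap in therapy") would miss late discontinuation if gaps were judged only inside 6 months, but the plan does not say that they are.
- Patients who start within 6 months of index have about 6 months of data left under the stated data period. Inclusion of later starters is unstated, not planned.
- On disenrolment, Limitations acknowledges that "if patients do not stay enrolled in the health plan through the outcome observation period, then their outcomes may be misclassified" and adds: "However, sensitivity analyses are planned to attempt to assess the impact of this bias".
- The 12-month version is optional: "Adherence and persistence may also be assessed at 12-months post-initiation based on results of 6-month measure".

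Each would benefit from a clarifying sentence, but none adds weight to this point.

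**Conclusion.** The point holds as a mismatch between a named measure and its stated formula. Followed literally, the formula can only equal or overstate days covered. In the constructed histories it gives up to 1.50 against 1.00, and 0.98 to 1.00 against 0.79 to 0.80 for a patient with a 37-day gap. This rests on summing supply over fills, a window of 180 to 184 days, and assumed fill sizes and dates. The direction of the error does not depend on those particular fill histories; its size does. Its frequency in this population cannot be derived from the documents.

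The consequence is confined to a descriptive secondary outcome; the primary outcome is unaffected. It should still be corrected, because the rule is wrong as written and the correction is nearly free.

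**What to change.** Replace the formula with a definition that matches the name:

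- Numerator: distinct days with any study drug on hand in a fixed window from first fill, with the window length stated in days.
- Denominator: that window length.
- Early-refill supply is carried forward only within the same drug or class (state which).
- Days covered by both classes count once.
- Supply is cut at the window end, and the maximum is 100%.

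The limit on carrying supply forward matters. If overlapping supply were carried forward across classes, three 30-day fills of both classes together would still score 98% to 100%, although only about half the days are covered.

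If the sponsor prefers the supply-based formula, rename it a possession ratio and state whether it is capped.

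The cost is a few lines of text and slightly more claims code, with no new data. Adherence figures will be equal to or lower than those from the present formula.

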A Pharmacy Quality Alliance (PQA) measure titled, “Use of Medications to Prevent Major Cardiovascular Events in Persons with Diabetes (CVDM)”, was voted on and approved by the membership in December 2020, is another strategy to help address this noted gap in effective care. However, complementary evidence-based initiatives are needed to communicate benefits of these medications to providers while simultaneously encouraging patients to engage in discussions with providers about their CV risk and ways to reduce future events.

As such, the purpose of this collaborative pilot is to test the impact of a dual educational intervention that includes communication to providers that their identified patients with T2DM and existing ASCVD may be candidates for guideline recommended medications, combined with communication to the identified at-risk patients regarding their CV risk.

STUDY METHODS

Study Objectives

The underutilization of ADA and ACC recommended treatments, specifically SGLT2i and GLP-1 RA medications with CV benefit, have been identified in the literature. In an effort to close this gap in the high-risk population of patients with T2DM and ASCVD, this pilot aims to inform select providers about the recent updates in guidelines regarding optimal treatment and also aims to inform patients about their risk and encourage discussions with providers about how to reduce their future risk of CV events.

Primary Objective

- Evaluate the impact of a dual educational outreach on 6-month frequency of SGLT2i and GLP-1 RA medication initiation by comparing patients and providers who receive and who do not receive the intervention.

Secondary Objectives

- Evaluate the impact of a dual educational outreach on 12-month frequency of SGLT2i and GLP-1 RA medication initiation by comparing patients and providers who receive and who do not receive the intervention.
- Evaluate the adherence and persistence to SGLT2i and GLP-1 RA medications 6-months after initiation. (Note: this outcome may also be assessed at 12-months post-initiation based on results of 6-month measure)

The hypothesis is that there will be a significantly greater (2% absolute increase) initiation of SGLT2i and GLP-1 RA medications with CV benefit among those who receive the educational outreach and message as compared to those who do not receive the intervention.

Data Source

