After the mailing (or fax) has been sent, a follow-up call to providers and patients will be conducted to ensure the message was received, reiterate the content of the initial outreach, and encourage discussions between patients and providers about CV risk reduction strategies. This call will be planned to take place within a few weeks (~3 weeks) from the initial mailing. While it will be requested to speak directly with the provider, nurses or other office staff may receive the call. Up to three call attempts will be made, with general messages being left asking for a return call if a voicemail is reached.

Three months after the initial outreach, another mailed/faxed communication will be sent to the providers reiterating the messaging from the first two communications, and including the list of patients who are still eligible for treatment and also noting those who have received treatment. The patients will also receive another direct mail communication approximately 3 months after the initial outreach reiterating the messaging from the first two communications.

The primary outcome for this study is the initiation of guideline-recommended SGLT2i or GLP-1 RA medications with CV benefit (excluding combination products) within 6-months of the initial outreach. Secondary outcomes include: 1) initiation of the medications of interest (excluding combination products) within 12 months of the initial outreach; 2) initiation of guideline-recommended SGLT2i or GLP-1 RA medications with CV benefit (including combination products) within 6-months of the initial outreach; 3) initiation of guideline-recommended SGLT2i or GLP-1 RA medications with CV benefit (including combination products) within 12-months of the initial outreach; and 4) adherence to SGLT2i or GLP-1 RA medications 6-months post-initiation; and 5) persistence to SGLT2i or GLP-1 RA medications 6-months post-initiation.

Identification and randomization: July 2021 (date on which data extraction begins)

Index event: date of first outreach to patients/providers (August 2021)

Second outreach (calls): start 3 weeks post-index

Third outreach (mailing/fax): starts 3 months post-index

[figure not shown]
Pre-identification and pre-index: 12-months continuous enrollment

Post-index: none

Follow-up: the primary outcome will be evaluated at 6-months and a secondary outcome will be utilization at 12 months post-index

Full data period: up to 2 years pre-index to 12-months post-index (July 2019 – August 2022)

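### Judged inside a 6-month window, the > 90 day gap rule cannot register stopping after about month 3, so the 6-month persistence figure is close to persistence to month 3

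*Combined protocol and SAP*

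**What the plan says.** The objective, under Study Objectives and again in the Statistical Analysis Plan, is: "Evaluate the adherence and persistence to SGLT2i and GLP-1 RA medications 6-months after initiation". Study Design lists as its fifth secondary outcome "persistence to SGLT2i or GLP-1 RA medications 6-months post-initiation".

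The Secondary Objectives part of the Statistical Analysis Plan gives the method:

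- **Timing and population:** "The adherence and persistence among those initiating SGLT2i and GLP-1 RA medications 6-months after the first medication fill will be described".
- **Construct:** "Persistence to the index medications will be defined as non-discontinuation of the treatment".
- **Gap rule:** "A patient will be considered non-persistent if there is a > 90 day gap in therapy and persistent if there are no gaps in therapy".
- **Persistent, in full:** "persistent if there are no gaps in therapy or gaps in therapy of ≤ 90 days".
- **Later assessment:** "Adherence and persistence may also be assessed at 12-months post-initiation based on results of 6-month measure".

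The timeline in Study Design ends the data at 12 months post-index (August 2022). The documents do not give the length of 6 months in days, a look-ahead past month 6, a rule for a gap still open at month 6, or a sensitivity analysis on the gap length.

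**The concern.** A gap of more than 90 days takes at least 91 uncovered days to observe, which is about half of a 6-month window. If the gap must be seen inside that window, a patient whose supply runs out in the second half cannot be scored non-persistent, even if nothing is ever filled again. The label promises persistence at month 6, while the rule registers only whether a long gap began in roughly the first three months.

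At stake is the meaning of a listed secondary outcome. A reader would take the figure as the share of initiators still on treatment at 6 months, and might use it to judge whether the outreach produces lasting use.

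**Working it through.** The documents state no persistence rate, so there is no figure to reproduce. The check is a count of days, followed by an illustration.

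**Inputs from the SAP:** window of 6 months from first fill; non-persistent only if the gap exceeds 90 days. **Input from Study Design:** data end 12 months post-index, taken as day 365. **Assumption:** 6 months is W = 180 to 184 days.

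**1. Latest run-out that can be flagged.** If supply runs out on day D and is not refilled, the gap visible in the window is W − D. Flagging needs W − D > 90, so D ≤ W − 91.

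| W | Latest D flagged | Share of window in which run-out is missed (91/W) |
|---|---|---|
| 180 | 89 | 50.6% |
| 182 | 91 | 50.0% |
| 183 | 92 | 49.7% |
| 184 | 93 | 49.5% |

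**2. Examples.**

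- Four 30-day fills, then permanent stopping: D = 120. The gap is 180 − 120 = 60 to 184 − 120 = 64 days, so the patient is persistent for every W. Proportion of days covered (PDC) is 120/180 = 67% to 120/184 = 65%.
- One 90-day fill, never refilled: D = 90. With W = 180 the gap is exactly 90, so persistent at a PDC of 50%. With W = 182 to 184 the gap is 92 to 94, so non-persistent. The unstated day count decides this case.

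**3. Direction.** Apply the same 90-day rule but let the gap complete after month 6. Everyone flagged inside the window is still flagged. Added to them are patients whose supply ended in about months 4 to 6 and who then went more than 90 days without a fill. The in-window figure can therefore only equal or exceed the figure under the plan's own definition.

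**4. Size, illustration only.** Let S(W) be the true 6-month persistence, with permanent stopping times following a Weibull curve of shape k. The rule reports S(W − 91) = S(W)^(((W − 91)/W)^k). With W = 180, (W − 91)/W = 89/180 = 0.494:

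| Shape k (assumed) | True 50% reported as | True 70% reported as | True 90% reported as |
|---|---|---|---|
| 0.5 | 61.4% (+11.4) | 77.8% (+7.8) | 92.9% (+2.9) |
| 0.7 | 65.5% (+15.5) | 80.4% (+10.4) | 93.8% (+3.8) |
| 1 (constant hazard) | 71.0% (+21.0) | 83.8% (+13.8) | 94.9% (+4.9) |
| 1.3 | 75.8% (+25.8) | 86.7% (+16.7) | 95.9% (+5.9) |

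With W = 183 every excess is smaller by 0.6 points or less.

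**5. Is there data for a look-ahead?** It needs W + 91 days after first fill: 271 (W = 180) to 274 (W = 183). With data ending on post-index day 365, only patients starting by day 365 − 271 = 94 or 365 − 274 = 91 have that much. To cover everyone starting within 6 months of index, the data must run to day 2W + 91. That is day 451 (W = 180) to 457 (W = 183), or 86 to 92 days beyond the stated end.

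**The case against.** **The text does not forbid a look-ahead.** The gap sentence does not say that the gap must be completed by month 6, and patients who start early have later claims available. This is fair, and the in-window reading is not the only possible one. It is the natural one, however, because the measure is described at 6 months and nothing directs the analyst further. If a look-ahead was intended, it must be written down, and the stated data period cannot support it for later starters.

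**A 90-day gap is a legitimate permissive choice.** Agreed. The fault is in pairing it with a window only about twice its length and calling the result 6-month persistence.

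**PDC over the same follow-up would show late stopping.** It would in part: the four-fill patient has a PDC of 65% to 67%, below the 80% cut. But PDC does not separate stopping from intermittent use, and persistence is listed as its own outcome.

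**The outcome is secondary and descriptive.** True. No between-arm test is planned for it, and the initiation outcomes are untouched.

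Four stronger readings are tempting, and the documents do not support them:

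- *The reported persistence must be too high overall.* Only the truncation effect has a fixed direction. The Limitations section notes that fills outside the available data are not seen and that disenrolment may misclassify outcomes; either can create a false gap.
- *Every patient whose first fill is a 90-day supply is persistent by construction.* This holds only for a 180-day window, which the plan does not state.
- *The overstatement is a known number of points.* No stopping rates are given.
- *The optional 12-month assessment will be wrongly triggered or dropped.* It depends on the 6-month result, but no criterion is stated, so this cannot be shown. Nor would that assessment correct the 6-month label. Anyone starting after index also lacks a full 12 months of data within the stated period.

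**Conclusion.** The point holds on the natural reading of the SAP, in which gaps are judged on claims within 6 months of first fill. Supply run-out after about day 89 to 93 can never be scored non-persistent, so the reported figure is close to persistence to month 3. Relative to the plan's own 90-day definition of discontinuation, this truncation can only raise the figure; the net direction of all errors together is not established.

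The day count rests only on a window of 180 to 184 days. The size is unknown. The illustrative excess of about 11 to 26 points at 50% true persistence, and 3 to 6 at 90%, rests on assumed Weibull shapes of 0.5 to 1.3 and permanent stopping. The result should be corrected or relabelled before it is reported. It does not bear on the primary comparison.

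**What to change.** 1. State the 6-month window in days.
2. Keep the 90-day gap. Date discontinuation at the last day of supply before a gap of more than 90 days, and classify 6-month persistence by whether that date falls before month 6, using fills up to about 91 days past month 6.
3. Restrict the analysis to patients initiating within 6 months of index.
4. Either extend the data period in Study Design by about 3 months, or use Kaplan-Meier, censoring patients whose look-ahead is cut short by disenrolment, death or end of data. For a patient with an open gap, state the censoring date. Censoring at the end of data beyond month 6 would carry that patient through as persistent and bring the fault back; the last day of supply avoids this. Patients censored with an open gap are likelier to be stoppers, so extending the data is the cleaner option.
5. If neither is possible, label the result as no > 90 day gap begun by about month 3.

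The cost is SAP wording, an amended data-period statement and about 3 more months of claims from the sponsor's own database. The secondary result would come slightly later, and the descriptive figure would be equal or lower. If patients initiating up to 12 months after index were included, the extension would be about 9 months (365 + 271 − 365 = 271 days). Relabelling alone needs no extra data.
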